### 2.5.3 Handling Missing Data

Every effort will be made to minimize the missing data in the study. We will record reasons for drop-out and compare baseline characteristics between participants who do and do not complete the study. However, since there are several scheduled visits following each transfusion, the investigators in this study can use regression analysis to predict and estimate 1-hour red cell post transfusion survival or mean lifespan based on the known red cell life span estimate of 120 days. Critical values for this estimation will be obtained on the day of blood donation and on day of RBC infusions. For this purpose, we will fit mixed effect models using 1-hour, 60 days and 120 days survival for non-missing observations including the subjects' characteristics. This model will be used to impute the missing value for other subjects of study. Alternatively, in at each time point a

prediction model will be created from patients' characteristics of non-missing observations to impute the missing data point per time of observation. These two approaches with complete set analysis will be compared.

#### **2.5.4 Data Management**

The study forms will be paper-based in that the data will be first recorded on paper forms at the time of the study visits. A relational database will be constructed on a local server with daily backups where only select research team members will have access to the database. The database will include data entry forms with the same appearance as the paper forms to facilitate accurate data entry and routine data edit checks for consistency both within and between forms. After data entry, the paper forms will be archived in secure file cabinets. All study subjects will be assigned unique study identifiers that will appear on all data collection instruments, documents, and files used in the statistical analysis and manuscript preparation. The case report forms with study IDs will be housed in the same chart as personal identifier documents are while the subject is active in the protocol. Only limited team members will have access to charts and database. No personal information concerning study participants will be released without their written consent. Other data quality assurance measures will include verifying the data, out of range data checks, and repeated evaluation of the data process.

The REDS-III RBC-OMICs subjects research records may contain the subject's SNP for the study team to know which SNP subgroup the subject is in.

### **3. HUMAN SUBJECTS**

The anticipated age range for the study population will be age 18 years or older based upon the target population. Healthy subjects of any ethnic background and with no significant past medical history will be eligible for enrollment.

The proposed study population will consist of potentially 223 (145 from the RBC-OMICs + 78 from Biotin infusion) healthy subjects. In order to achieve this number, it is anticipated that approximately 231 (145 from RBC-OMICs + 86 from Biotin infusion) participants may need to be enrolled into this study to account for subjects who may not qualify the eligibility criteria or not be able to donate blood or are withdrawn for any reasons.

#### **3.1 SUBJECT POPULATION**

##### **3.1.1 Inclusion of Women and Minorities**

Women and individuals from minority groups especially African Americans or individuals originally from malaria endemic regions who meet the inclusion criteria, and have none of the exclusion criteria, will be enrolled without restriction as dictated by the study protocols. Every effort will be made to enroll participants in this research in a distribution, which mirrors the study population of the Pittsburgh area.

##### **3.1.2 Inclusion of Children**

This investigation will not enroll children based upon lack of safety data in children with regards to the investigational product.

### 3.1.3 Inclusion of Prisoners

This investigation will not enroll prisoners.

## 3.2 INCLUSION CRITERIA

The following criteria will be required on ALL subjects:

- Male or female age 18 years or older at screening.
- Weight  $\geq$ 110 lbs.
- Hemoglobin at or above 12.5 g/dL or hematocrit  $\geq$  38% for women and hemoglobin  $\geq$  13.0 g/dL or hematocrit  $\geq$  39% for men.
- Meet screening criteria for autologous blood donation

### Additional Inclusion Criteria for Other Sub-Groups:

#### Healthy volunteers ( subjects who complete the study=20)

- 10 males and 10 females
- Caucasian

#### Healthy African American volunteers with sickle cell trait ( subjects who complete the study=15)

- Self-identification of African American race
- Sickle cell trait (HbAS) status confirmed by hemoglobin electrophoresis

#### Healthy African American volunteers without sickle cell trait (subjects who complete the study=20)

- 10 males and 10 females
- Self-identification of African American race
- Normal Hb (HbAA) and sex and age match to HbAS donors

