## **1.4 SIGNIFICANCE**

The quality of a unit of stored RBC for transfusion, a procedure performed about 12 million times per year in patients, is currently based on levels of storage hemolysis. However, the storage lesion is a singular manifestation of a multitude of injuries that occur during red cell storage. Hemolysis measures alone failed to capture the progressive accumulation of these changes, some of which may affect the ability of transfused red blood cells to traverse the microcirculation. Furthermore, there is limited data on the correlation between *in vitro* measures of hemolysis and post-transfusion survival of stored red blood cells. This project explores the current gaps in understanding the impact of genetic and biologic factors in blood donors on red blood cell storage stability and post transfusion recovery. We also seek to determine whether *in vitro* markers of storage integrity can predict red cell survival in the patient circulation.

Our studies in human and animal models have demonstrated that genetic variability and biological variables such as sex, age, race or iron availability may significantly modulate predisposition to hemolysis under diverse stress conditions including routine cold storage of RBC units, and in hemolytic disease. For example, we have shown that RBCs from male donors (human or mice) exhibit higher susceptibility to hemolysis during storage, and under osmotic, mechanical or oxidative stress. Furthermore, we have demonstrated the effect of donor sex, testosterone or sickle cell trait on RBC storage and post-transfusion recovery in a murine model of transfusion. As members of NHLBI REDS-III and collaborators on the RBC-Omics project, we have further demonstrated in 13,403 informed blood donors that variables such as sex, race, and donation intensity may modulate RBC hemolytic response to cold storage and to osmotic and oxidative stress. Having completed the screening of these donors for hemolytic propensity, we are currently seeking for genes that mediate hemolysis using genome-wide association approach. The biotin method would provide us the unique opportunity to verify whether our *in vitro* correlates of hemolysis or the newly discovered genes may predict RBC recovery *in vivo*.

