## 2.5 STATISTICAL ANALYSIS

### 2.5.1 Sample Size Determination

In healthy volunteers, the mean (SD) of 30 and 60-days RBC biotin recovery rate is 75% (12.5%) and 50% (10%) (calculated from 24-hour 100% recovery value), respectively. For our first study, evaluating patients with the sickle cell trait SNP, we expect SCD trait to reduce 30 and 60-day recovery to 62% and 25%. A sample size of 15 subjects with sickle cell trait (HbAS) and 20 control African American subjects (HbAA; 10 males and 10 females) would provide 84% power to detect a difference of 13% (SD =12.5%) for 30 days and a power of >95% to detect a difference of 25% (SD = 12.5%) for 60 days RBC recovery rate between AS and AA. This sample size has at least 80% power to detect the interaction between time and genetic group as measure of different recovery rate. We will also recruit an additional 20 Caucasian control (HbAA, 10 males and 10 females) to gain power for testing the effect of other RBC mutations identified in our genome-wide association studies of blood donors (NHLBI RBC-Omics). We will use explanatory analysis for the evaluation of post transfusion recovery of RBCs from subjects with rare variants (<10% of the population) due to a projected small number of subjects carrying such mutations. All 40 control subjects will be tested and selected to not have any of the SNPs that we are studying (listed below).

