This power calculations informs our other planned studies that will compare up to 7 additional single nucleotide polymorphisms (SNPs) patient groups of 15 each, compared with our control groups without the SNPs (n=20 race and gender matched). Successful enrollment of the sickle trait and 7 SNP groups would be 120 total subjects. The eight genetic mutations that we will evaluate may include sickle cell trait (AS), and single nucleotide polymorphisms (SNPs) in ankyrin 1 (ANK1), glucose-6-phosphate dehydrogenase X-linked (G6PD), piezo-type mechanosensitive ion channel component 1 (PIEZ01), spectrin alpha (SPTA), extended synaptotagmin-like protein 2 (ESYT2), Myo9b and SEC14. We may identify additional SNPs as our analysis of the REDS-III GWAS study advances that could replace one of these SNP groups and/or we identify additional non-synonymous SNPs that are associated with susceptibility to hemolysis of stored red blood cells. In addition, we will evaluate 15 subjects on testosterone replacement therapy with 20 controls that are gender and race matched that are not on testosterone replacement therapy.

Each study will be conducted as an independent analysis of 15 subjects with the SNP and 20 race and gender matched subjects without the SNP using power calculations estimated from the SCD trait example above.

**Biotin infusion study:** The study team will target 70 evaluable subjects. The study team will approach 86 subjects with 90% expected to agree to yield 78 subjects who will sign the biotin infusion consent. The study team expects 90% of these subjects to complete the biotin infusion study yielding the target 70 evaluable subjects. The biotin infusion subjects include 20 Whites, 20 African American without sickle cell trait, 15 African Americans with sickle cell trait, and 15 males on testosterone. In addition, 20 subjects with SNPs from the REDS-III RBC-OMICS study will be included for a total of 98 subjects to sign the biotin infusion consent and yield approximately 90 subjects who complete the study.

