### 2.5.2 Statistical Analysis

The primary assessment of RBC transfusion efficacy is post transfusion survival. Data from RBC recovery at 2-4 hours, 1 month and 2 months after each transfusion will be evaluated using mixed effect model (with restricted maximum likelihood variance estimator and bootstrapping) to calculate the effect of time, genetic group and their interaction on RBC survival. RBC recovery at each time point will be performed using the equation below.

$$\text{Percent survival (\%)} = \frac{\text{BioRBCs in circulation at } T_y \text{ (} 1 \leq y \leq 120 \text{ days)}}{\text{Baseline BioRBCs in circulation at } T_0 \text{ (20 min following RBC infusion)}} * 100$$

Secondary endpoints: The equation above will be used to define the 2-4hours post transfusion survival of BioRBCs. The other endpoints test for changes in RBC predisposition to hemolysis in cold storage by quantifying the rates of storage, osmotic, mechanical and oxidative hemolysis and the formation of RBC membrane-derived microvesicles. A sample size of 8 samples would detect a 10% difference in our assays' outputs with a power of 85%. We will use commercial software for statistical analyses (STATA version 15.0, StataCorp., College Station, Texas, USA). We will use mixed effect model (with restricted maximum likelihood variance estimator and bootstrapping) to calculate the effect of time, genetic group and their interaction on RBC survival. Normality tests will help to determine the appropriate transformation of outcome data. We will also use nonlinear term of time in these models (if applicable). We will use marginal test (from the primary models) to assess the effect of genetic group on 60-days and 2-4hours RBC survival separately. As a confirmatory analysis, Wilcoxon signed rank test will determine the differences between two groups for 60-days and 2-4 hours survival rate as well. The hypotheses will be tested primarily in old blood. A separate analysis will be performed in fresh blood transfusion as well. All P value <0.05 will be reported as statistically significant.

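### The sex mix of the sickle-trait subjects is not tied to that of their controls, age is not matched in the testosterone comparison, and the primary model adjusts for neither.

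*Combined protocol and SAP*

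**What the plan says.** Section 3.2 (additional criteria by sub-group) sets two sex rules for the 20 African American controls without the trait: "10 males and 10 females", and "Normal Hb (HbAA) and sex and age match to HbAS donors". For the 15 trait subjects it lists only "Self-identification of African American race" and HbAS status on electrophoresis, with no sex quota and no age band. Section 2.5.1 repeats the even split for the controls and gives none for the trait group. No matching ratio or tolerance is stated.

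For testosterone, section 2.5.1 plans "15 subjects on testosterone replacement therapy with 20 controls that are gender and race matched"; age is not mentioned there or wherever else the comparison is described. The treated group is men only. Entry is at 18 or older with no upper limit, and the Caucasian controls have no age rule.

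Section 1.4 states that "biological variables such as sex, age, race or iron availability may significantly modulate predisposition to hemolysis". The synopsis names donor sex as a variable that might affect recovery itself, and the hypothesis in section 1.2 includes sex. The primary mixed model in section 2.5.2 is fitted "to calculate the effect of time, genetic group and their interaction on RBC survival". Subject characteristics appear only in the missing-data models of section 2.5.3.

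**The concern.** The groups are not randomised, so comparability depends on matching and on the model. In the sickle-trait comparison, from which the power statement is built, the controls have a fixed sex split while the group they should resemble has none. If the trait group enrols mainly one sex, the two control rules pull apart, and section 2.5.1 lists no other African American infusion controls without the trait. Any effect of sex on recovery would then enter the estimated trait effect.

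The testosterone comparison has a different gap. Sex is controlled there, but age is left open by both the matching rule and the model. In both comparisons the uncontrolled variable is one that the protocol itself treats as a possible modulator.

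**Working it through.** **1. The plan's own figure.** Inputs from section 2.5.1: 15 versus 20 subjects, SD 12.5, difference 13 points at 30 days. The test level is 0.05 (section 2.5.2), taken as two-sided.

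- SE = 12.5 × √(1/15 + 1/20) = 4.27.
- Noncentrality = 13 / 4.27 = 3.04 on 33 degrees of freedom. Power of the two-sample t-test = 84.0%, which agrees with the stated 84%.
- For 25 points at 60 days, power exceeds 99.9%, consistent with the stated figure of more than 95%. The power statement is not in dispute.

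**2. When the two control rules agree.** Fifteen is odd, so an exact half-and-half trait group is impossible; 7 or 8 men is closest. One-to-one matching of 15 controls from 10 men and 10 women needs at most 10 trait men and at most 10 trait women, that is, 5 to 10 men. The number of men among 15 is taken as binomial; the probability is an assumption.

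| P(male) | 7 or 8 men | 5 to 10 men | Outside 5 to 10 |
|---|---|---|---|
| 0.5 | 39% | 88% | 12% |
| 0.4 or 0.6 | 30% | 77% | 23% |
| 0.3 or 0.7 | 12% | 48% | 52% |

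**3. Size of a sex imbalance.** Shift in the unadjusted trait estimate = (male share in trait group − 0.50) × sex effect. The documents give no sex effect on recovery, so 5 to 10 points is assumed, with men's cells recovering less.

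- 4 men of 15: (0.267 − 0.50) × 5 or 10 = −1.2 or −2.3 points, hiding part of a true deficit.
- 12 men of 15: (0.80 − 0.50) × 5 or 10 = +1.5 or +3.0 points of false deficit.
- With 12 men and no trait effect, the 5% error rate becomes about 6.3% or 10.5%.

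The largest of these shifts, 3.0 points, is 0.7 of the SE (3.0/4.27), 23% of the 30-day difference (3.0/13) and 12% of the 60-day difference (3.0/25).

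**4. Cost of adjustment.** Least-squares SE of the group effect with sex in the model, residual SD kept at 12.5, 13-point effect:

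| Trait men | SE | Power |
|---|---|---|
| 7 or 8 | 4.27 | 83.9% |
| 5 or 10 | 4.33 | 82.9% |
| 3 or 12 | 4.49 | 80.2% |
| 0 or 15 | 5.10 | 69.5% |

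**5. Testosterone controls.** The infusion cohort in section 2.5.1 lists no separate testosterone controls. Its two control groups hold 10 + 10 = 20 men. Twenty male controls therefore means every control man of both races, which leaves nobody to select by age. No age distribution and no age effect is given, so no bias can be computed.

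**The case against.** A reader might infer that the two control rules contradict each other. They do not. The match is undefined, and one-to-one matching works in about 88% of draws under even recruitment. Section 3.1.1 also aims for enrolment that reflects the local population, which makes extreme splits less likely, although it sets no target for this group. What remains is that the plan neither requires a workable split nor says which rule yields.

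A reader might also infer that both sex and age are open in each comparison. The text does not support this. Age matching is stated for the trait comparison and sex matching for the testosterone comparison, so each has one gap.

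The illustrated imbalances are tail cases. Under even recruitment, 4 or fewer men has probability 5.9% and 12 or more has 1.8%. The sex effect is assumed: the human data described in section 1.4 concern hemolysis, and the recovery evidence is from mice. The 60-day difference, closest to the primary endpoint, is less exposed. All of this stands and limits the size of the point.

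It is tempting to add that testosterone users will be older, so that age would pass for a treatment effect. The documents do not say so. Section 3.2 stresses growth among patients aged 18 to 45, and the exclusions for cardiovascular and metabolic disease may narrow the age range.

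Finally, the synopsis and section 2.4 plan analyses of gender. These would make an imbalance visible, but they do not adjust the primary contrast.

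**Conclusion.** The point holds in a limited form. Sex can differ between trait subjects and their controls because the trait group's sex mix is unspecified and no precedence between the two control rules is given. Age can differ in the testosterone comparison. The primary model corrects for neither.

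Under an assumed 5 to 10 point sex effect, 4 or 12 men among 15 moves the trait estimate by 1.2 to 3.0 points. That is smaller than its standard error of 4.27 and well below the planned 13 and 25 points. The probability of an imbalance that large depends on an assumed recruitment mix. The testosterone age bias has no derivable size or direction. This is a gap worth closing because the remedy is almost free; it does not show that the planned comparisons are invalid.

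**What to change.** - **Model (section 2.5.2).** Pre-specify sex, where both sexes are present, and age at donation as covariates in each group comparison. State whether they also interact with time, because a main effect alone does not adjust the group-by-time term.
- **Sex rules (section 3.2).** Reconcile the trait and control criteria: either fill the African American controls to the observed sex mix of the trait group, or set a target of 7 to 8 of each sex for the trait group. Say which rule governs.
- **Testosterone comparison.** Do not require age matching. With only 20 control men listed there is no room to select, and re-matching the African American men would compete with their age match to trait subjects. Handle age by the covariate.

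Cost: one or two degrees of freedom in a 35-subject comparison. Demographics are already collected at Visit 1. With sex in the model, power for 13 points is 83.9% with 7 or 8 trait men and 80.2% with 3 or 12. It falls to 69.5% only if the trait group is all one sex. A sex target could slow recruitment of trait subjects slightly; filling controls to the observed mix avoids that.

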#### Healthy volunteers enrolled in REDS-III Red Blood Cell Omics (RBC-Omics) study (105=subjects who complete the study)

- Recalled blood donors from the RED-III RBC-Omics study with non-synonymous SNPs identified in ANK1, G6PD, PIEZ01, SPTA, ESYT2, Myo9b, SEC14 and/or we identify additional non-synonymous SNPs that are associated with susceptibility to hemolysis of stored red blood cells. We may identify additional SNPs as our analysis of the REDS-III GWAS study advances that could replace one of these SNP groups. The SNPs will be tested for functional effects on red cell biophysical properties, stability in storage, and release of eDAMPs, compared to donors with no implicated SNPs. We will develop an enriched SNP profile that defines a high risk and low risk donor for further evaluation as a low cost precision transfusion medicine array. As determined in the aforementioned primary and secondary endpoints.

#### Healthy Volunteers Receiving Testosterone Replacement Therapy (subjects who complete the study=15)

- Male only

We aim to determine the impact of testosterone replacement therapy (TRT) on transfusion safety by defining the post transfusion recovery of stored biotinylated-RBCs from male donors who receive TRT. TRT has been recently identified as one of the most overused medical practices in the US, with a 4-fold increase in the number of young patients (ages 18-45) since 2003. The lack of clear guidelines and risk assessment of RBC transfusion from TRT patients deem such donors eligible for donation, except for cases of suspected polycythemia. We have shown that TRT in mice enhances predisposition to osmotic and oxidative stress, whereas orchiectomy is associated with improved post transfusion recovery of stored RBCs as compared with intact males. This study will verify whether the negative impact of TRT on RBC storage stability observed in mice is clinically relevant in transfusion of blood from TRT donors.

### **3.3 EXCLUSION CRITERIA**

Subjects meeting any of the following exclusion criteria at baseline will be excluded from participating in study:

- Subjects with a past medical history or symptoms of blood dyscrasia, diabetes mellitus, hyperlipidemia, obstructive sleep apnea, renal disease, congestive heart failure, significant cardiac disease and / or known peripheral arterial disease.
- Moderate to severe systemic hypertension, (systolic blood pressure >140 mmHg and/or diastolic blood pressure > 95 mmHg)
- Systolic blood pressure <100 mmHg and/or diastolic blood pressure < 60 mmHg on the study day.
- Positive Direct Antiglobulin Test (DAT)
- Consumption of biotin supplements or raw eggs within 30 days
- Treatment with antibiotics in the week before initiating study participation to avoid suppression of erythropoiesis, which may accompany infection.
- Blood loss in the previous 8 weeks due to epistaxis, trauma, hemoptysis, gastrointestinal bleeding, diagnostic phlebotomy (> 30ml)
- Subjects who report tobacco or marijuana smoking within 6 months of study.
- Cognitively impaired subjects, or institutionalized persons and subjects unable or unwilling to complete written informed consent
- Subjects with a history of blood donation within the last 56 days.
- Use of other investigational drugs/devices within 30 days of screening.
- Subjects taking any medication for the treatment of diabetes including insulin
- Females of childbearing potential who are pregnant or unwilling to undergo pregnancy testing; females with positive pregnancy testing on screening day will be excluded.
- History of prior transfusion reaction to blood products.
- Allergic reaction to biotin
- Donors with naturally occurring antibodies against BioRBCs will be excluded from the study

